#### 10.6.5 Safety Analyses

All safety analyses will be performed on the safety population. The primary safety analysis will summarize ocular and non-ocular treatment-emergent AEs (TEAEs) using discrete summaries at the subject level by system organ class and preferred term for each treatment group. Ocular TEAEs will be summarized separately for all study and fellow eyes. A TEAE will be defined as occurring after the first dose of study medication. Serious adverse events and treatment-related ocular and non-ocular TEAEs will be summarized similarly. Ocular and non-ocular TEAEs will also be summarized by severity.

Slit lamp biomicroscopy and dilated indirect ophthalmoscopy measures will be summarized at each visit using discrete summary statistics.

Intraocular pressure will be summarized at each visit, using continuous and discrete summary statistics, including change from baseline and the proportion of study eyes with an increase from baseline in IOP of 10 mmHg or more and the proportion of study eyes with IOP of 30 mmHg or more.

Safety laboratory data will be summarized at each visit, using continuous summary statistics, including change from baseline.

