#### 8.2.2 Escape Medications

If IOP rises above 25 mmHg a topical prostaglandin analog will be considered. If IOP rises above 32 mmHg, the study drug will be discontinued, (DexNP or vehicle eye drops) and the IOP treated with glaucoma drugs or other treatment at the discretion of the study ophthalmologists.

If BCVA drops by 10 letters or more or CMT increases by 20% or more at 2 consequent visits and the changes are judged by the treating physician to be due to DME the patient should be stopped to receive the DexNP or vehicle experimental eye drops and may be treated at the discretion of the investigator with standard of care, i.e. anti VEGF injections or steroid implant. The patient should be asked to return for all scheduled control visits, even if the study drug has been discontinued

If BCVA drops by 10 letters at 2 consequent visits and the decrease in vision is felt by the treating physician to be due to cataract formation the patient shall be offered cataract surgery and IOL implantation. The patient stays in the study and continues with eye drops as indicated by the protocol.

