### **10.5 Study Populations**

*ITT Population:* The intent-to-treat (ITT) population will consist of all randomized subjects, analyzing subjects under the treatment to which they were randomized.

*PP Population:* The per-protocol (PP) population is a subset of the ITT population and includes subjects who do not deviate from the protocol in any way likely to seriously affect the primary outcome of the study, analyzing subjects under the treatment actually received. Important protocol deviations related to study inclusion or exclusion criteria,

conduct of the trial, subject management, or subject assessment will be identified prior to unmasking treatment.

*Safety Population:* The safety population includes all randomized subjects who receive at least one dose of study medication. The safety population will be analyzed as treated and will be used for the safety analyses. No data will be excluded for any reason.

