#### 10.6.4 Secondary Efficacy Analyses

Change from baseline in ETDRS BCVA letters to Weeks 2, 4, 8, and 16 and ETDRS BCVA letters at Weeks 2, 4, 8, 12, and 16 will be analyzed similarly to the primary efficacy analyses using ODO on the ITT population.

Mean and mean change in central retinal subfield thickness will be analyzed similarly to ETDRS BCVA.

The proportion of study eyes a) gaining at least 10 or 15 letters BCVA and b) losing at least 15 letters will be summarized using discrete summary statistics. Treatment comparisons will be completed using Pearson's chi-squared statistic, with Fisher's exact statistic used for any comparison with an expected cell frequency of 5 or less. Confidence intervals (70%, 90%, and 95%) will also be presented for each treatment group and the difference between treatment groups, using asymptotic or exact methodology as consistent with the employed testing procedure. The analyses will be completed primarily on the ITT population and secondarily on the PP populations using ODO.

In all of these analyses, data from subject visits after receipt of rescue medication will be imputed using last observation prior to receiving rescue medication for continuous endpoints and will be imputed as failures for success/failure variables.

The VFQ-25 measurements will be summarized using continuous summary statistics for the total score, subscale scores, and each individual question score using observed data only. Imputation of missing individual question scores in calculating subscale and total scores will be detailed in the formal statistical analysis plan and will follow methodology used in developing the instrument.

One-sample t-tests will be used to primarily analyze the mean change from baseline within a treatment group; additionally, the non-parametric Wilcoxon signed-rank test will be used secondarily to analyze the change from baseline. Two-sample t-tests will be used to primarily analyze the difference in the mean scores between treatments at each visit and change from baseline; additionally, the non-parametric Wilcoxon rank-sum test will be used secondarily to analyze the differences in scores between treatments.

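### Safety summaries are never cut at rescue, so specific steroid or procedure events and visit-level IOP can reflect rescue treatment rather than the study drops; supplementary pre-rescue tables would separate the two cheaply

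*Combined protocol and SAP*

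**What the plan says.** **Rescue.** Section 8.2.2 sets the DME trigger: "If BCVA drops by 10 letters or more or CMT increases by 20% or more at 2 consequent visits", with the change judged by the treating physician to be due to DME. The drops then stop and the patient "may be treated at the discretion of the investigator with standard of care, i.e. anti VEGF injections or steroid implant". The rule applies to both arms. Follow-up continues: "The patient should be asked to return for all scheduled control visits, even if the study drug has been discontinued".

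**Safety.** Section 10.5 states "The safety population will be analyzed as treated and will be used for the safety analyses", and then "No data will be excluded for any reason". Section 10.6.5 sets the start of the event window ("A TEAE will be defined as occurring after the first dose of study medication") but no end. It tabulates TEAEs by system organ class and preferred term at subject level. IOP is summarised at each visit, including "the proportion of study eyes with an increase from baseline in IOP of 10 mmHg or more" and the proportion at 30 mmHg or more. Rescue is not mentioned.

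**Efficacy.** Section 10.6.3 replaces the Week 12 BCVA of a rescued subject with the last value before rescue. Section 10.6.4 does the same for the other BCVA and CMT analyses ("data from subject visits after receipt of rescue medication will be imputed using last observation prior to receiving rescue medication") and counts rescued subjects as failures for success/failure variables. The VFQ-25 is the exception, being summarised on observed data.

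**The concern.** The drug under test and one of the two rescue options are both corticosteroids. The Introduction (Safety profile) and section 8.10 name cataract, raised IOP and infection as the class risks. The Introduction also lists infection, haemorrhage and cataract as complications of intravitreal injection and implantation. A vehicle eye given a steroid implant can therefore add steroid effects to the comparator column, and an injection complication is counted under whichever drop the eye had been using.

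The DexNP side can blur as well. In the earlier 12-patient DME trial described in the Introduction, IOP was 7 ± 7 mmHg above baseline at 12 weeks on DexNP, and 1 ± 6 mmHg above baseline four weeks after stopping. A DexNP eye that stops its drops and is rescued with anti-VEGF may drift back towards baseline while still contributing to the DexNP visit summaries.

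Safety is the second study objective (section 2) and the second clinical hypothesis (section 3). What is at stake is how well the tables show the steroid effects of the drops themselves, mainly on IOP.

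**Working it through.** **1. How much follow-up can be post-rescue.** The trigger needs two visits in a row. Post-baseline visits are at Weeks 2, 4, 8, 12 and 16 (Appendix 1), so the earliest scheduled visit at which it can be met is Week 4. Post-rescue time can then run for 16 − 4 = 12 of 16 weeks (75%).

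**2. Denominators.** Section 5.1 gives 64 DexNP and 32 vehicle subjects. The sample-size calculation behind them reproduces: with a 3.5-letter difference, SD 8, one-sided alpha 0.15, 2:1 allocation and one O'Brien-Fleming-type interim at 50%, power at 58 + 29 is 80.6%. Allowing for 10% dropout, 87/0.9 = 96.7, against 96 stated. One extra subject with a given preferred term adds 1/32 = 3.1 points on vehicle and 1/64 = 1.6 points on DexNP.

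**3. IOP contrast.** The plan gives no rescue rate and no safety figure to reproduce, so this is an illustration. Let
- p_V = vehicle rate of an IOP rise of 10 mmHg or more without rescue;
- p_D = the same rate on DexNP;
- p_R = the rate after a steroid implant;
- r = share of vehicle eyes rescued;
- s = share of those rescues done by implant.

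The vehicle rate in the uncut table is p_V + r·s·(p_R − p_V). If p_R = p_D and only vehicle rescues are counted, the uncut difference is (p_D − p_V)(1 − r·s). The relative attenuation is r·s, whatever p_V is.

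Assumed inputs: p_D from a normal distribution with the earlier trial's mean 7 and SD 7, so p_D = 1 − Φ((10 − 7)/7) = 33.4%; p_V = 2%. Cut at rescue, the difference is 33.4 − 2.0 = 31.4 points. Uncut:

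| Vehicle eyes rescued | All by implant | Half by implant |
|---|---|---|
| 5% (1.6 of 32) | 29.8 | 30.6 |
| 10% (3.2) | 28.3 | 29.8 |
| 20% (6.4) | 25.1 | 28.3 |
| 30% (9.6) | 22.0 | 26.7 |

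Relative attenuation runs from 0.05 × 0.5 = 2.5% to 0.30 × 1 = 30%.

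**4. A rough guide to the rescue rate.** Take the plan's SD of 8 letters, and assume a mean change of 0 on vehicle and +3.5 on DexNP at every visit, with an equal correlation of 0.5 to 0.85 between visits. A loss of 10 letters or more at two consecutive visits in Weeks 2 to 12 then occurs in about 7% to 10% of vehicle eyes and 2% to 4% of DexNP eyes. The CMT trigger would add an unknown amount. Physician attribution to DME and the optional nature of treatment would subtract.

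**5. Overall ocular TEAE rate.** Suppose 15% to 25% of vehicle and 5% to 10% of DexNP eyes are rescued, and 30% to 50% of rescued eyes have an ocular event caused by rescue (all assumed). If no rescued eye already had an ocular TEAE, the vehicle-minus-DexNP shift would be:
- same event rate in both arms: from (15% − 10%) × 30% = 1.5 points to (25% − 5%) × 50% = 10 points;
- event rates free to differ by arm: from 15% × 30% − 10% × 50% = −0.5 points to 25% × 50% − 5% × 30% = 11 points.

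The sign is not fixed. These figures also overstate the shift. TEAEs are counted once per subject, and section 9.1 makes any clinically relevant deterioration in a clinical finding a recordable AE. An eye that has worsened enough to be rescued will usually have an ocular TEAE already, and a later rescue event then adds nothing to the any-event row.

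**The case against.** **All-data safety reporting is legitimate.** This stands. Section 10.6.5 is descriptive, and efficacy and safety may properly use different data rules. The gap is a missing second summary, not an error in the first.

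**The plan already mitigates.** Treatment-related TEAEs are tabulated, AE dates and actions are recorded (section 9.1), and concurrent medications are recorded with their reasons (section 8.2), so a split could be made later. This stands in part. Relatedness is the investigator's judgement (section 9.1.2) and does nothing for the IOP, slit-lamp or ophthalmoscopy summaries. A split made later is not a planned one.

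**As-treated analysis might move the eye.** No rule does so. Rescue is not study medication, so the events stay with the study-drop arm.

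**A later plan may cover it.** Section 10.6.4 refers to a formal statistical analysis plan for VFQ-25 scoring. Nothing in this document says that plan will add a safety cut.

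**Stronger readings that the documents do not support.** A reader might infer that post-rescue harms raise the overall vehicle ocular TEAE rate by several points, or that the error always favours DexNP. The first overlooks subject-level counting and the AE definition. The second needs rescue rates and rescue types by arm, which are not given: DexNP eyes can be rescued too, and anti-VEGF events could push either way. A reader might also infer that pre-rescue tables should replace the all-data ones as the basis for comparison. That would censor at an outcome-related event. If vehicle eyes are rescued more often, they lose more follow-up, and crude vehicle counts would fall for that reason alone.

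**Conclusion.** The point holds as a cheap improvement. No planned safety summary separates time on study drops from time after rescue, and one rescue option belongs to the class under test. Individual preferred terms and IOP by visit are where this can show. A vehicle eye given an implant narrows the IOP contrast.

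Under the assumptions in step 3 the narrowing is 2.5% to 30% in relative terms. It is small when either the rescue rate or the implant share is small, and zero if no vehicle eye receives an implant. The illustration rests on assumed rescue and implant shares, on implants raising IOP as often as DexNP, and on leaving DexNP rescues out. The absolute points rest further on a normal approximation from 12 patients whose drops were tapered from three to one a day. The net direction across all safety tables is conditional on rescue rates by arm, and the overall any-ocular-TEAE rate may hardly change.

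**What to change.** In section 10.6.5:

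1. Keep the all-data tables as the main safety summary.
2. Add supplementary study-eye tables of ocular TEAEs by preferred term, restricted to onset before first rescue in the study eye, with time at risk and exposure-adjusted rates by arm.
3. Add the study-eye IOP summaries restricted to visits before first rescue.
4. List post-rescue events by study-drop arm and rescue type (anti-VEGF or steroid).
5. Present the two sets side by side, noting that follow-up to rescue may differ by arm. State that rescue here means DME rescue, since section 8.2.2 also covers IOP treatment.

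The cost is analysis-plan wording and one extra set of tables. The first-rescue date is already needed for sections 10.6.3 and 10.6.4. The downside is shorter follow-up in the restricted set, possibly unequal between arms because rescue is related to outcome; time at risk addresses unequal length but not that selection. Sample size, endpoints and the rescue rule are unchanged.

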### 8.2 Concurrent Therapies

The use of any concurrent medication, prescription or over-the-counter, is to be recorded on the subject's source document and corresponding case report form (CRF) along with the reason the medication was taken.

Concurrent use of other eye drops is not allowed. Should concurrent treatment with IOP lowering eye drops (prefer prostaglandin) become necessary due to increased IOP, those eye drops should be administered in the evening 15 minutes before DexNP/Vehicle eye drops.

Other treatments for DME are not allowed in the study eye while the patients are included in the study except if they meet the rescue criteria as described in 8.2.2 below.

If the fellow eye needs any treatment for DME or any other conditions, standard of care (i.e. anti-VEGF for DME) can be applied except steroids. So i.e. Ozurdex or topical dexamethasone will not be allowed for the treatment of the fellow eye during the course of the study.

The use of contact lenses is NOT allowed during the active study treatment phase of 12 weeks.

Concurrent enrollment in another investigational drug or medical device study is not permitted.

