### 8.3 **Examination Procedures**

#### 8.3.1 Procedures to be performed at Each Study Visit with Regard to Study Objective(s)

A complete eye examination will be performed. (Detailed descriptions may be found in an optional study manual if deemed necessary by the sponsor)

- Visual acuity will be measured at every visit using ETDRS chart at 4m with best corrective lenses.
- Intraocular pressure (IOP) will be measured at every visit with Goldmann tonometry or I-CARE tonometry (standardized in each center and the same device to be used for a given patient throughout the study)
- Eye examined at every visit by slitlamp.
- Fundus is examined at every visit through dilated pupils (i.e. using Tropicamide hydrochloride 1% and phenylephrine 2.5%),
- Fundus photographs obtained (optional)
- Optical coherence tomography (SD OCT preferably using Heidelberg Spectralis) performed at each visit to measure central macular thickness (CMT).
- In phakic eyes cataract formation will be graded using the LOCS III system.
- Irritation will be evaluated at every visit by slit lamp biomicroscopy, fluorescein staining when deemed necessary

- Blood pressure should be measured on the patient sitting for at least 2 minutes, on the right arm.
- Quality of life as assessed by NEI VFQ-25 at baseline and 12 weeks.

The full eye examination will be performed before start of the study at screening and then at each visit (Day 1, weeks 2, 4, 8, 12 and 16) until end of the study period.

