#### 8.4.2 Unscheduled Visits

Unscheduled visits are possible at every time and will be documented in the respective CRF.

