#### 8.6.2 Discontinued Subjects

Subjects may be discontinued prior to their completion of the study – either discontinue study medication or completely leave the study (i.e. due to loss of follow-up). Patients who discontinue study medication generally should be followed through to the final visit.

Reasons for discontinuation may be:

- adverse events
- protocol violations
- lack of efficacy
- administrative reasons (eg, inability to continue, lost to follow up)
- sponsor termination of study
- other

Note: In addition, any subject may be discontinued for any sound medical reason and the study subjects are free to discontinue the study participation on their discretion.

Notification of a subject discontinuation and the reason for discontinuation will be made to IRW and/or study sponsor and will be clearly documented on the CRF.

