## 9 ADVERSE EVENTS

### 9.1 Adverse Event

An adverse event is defined as any untoward medical occurrence in a participating patient associated with the use of an investigational medicinal product (IMP) which does not necessarily have a causal relationship with IMP. An adverse event can be any unfavorable and unintended sign (e.g., an abnormal laboratory finding), symptom, or disease temporally associated with the use of an investigational product and judged by the Investigator as clinically significant.

All AEs are reported by the subject and/or in response to an open question from study personnel or revealed by observation, physical examination or other diagnostic procedures will be recorded in the source document and on the AE pages eCRF. Any clinically relevant deterioration in clinical finding is considered an AE and must be recorded. When possible, signs and symptoms indicating a common underlying pathology should be noted as one comprehensive event.

Documentation and evaluation regarding the adverse event should be made as of:

- type of event
- seriousness
- degree of severity
- duration (start - end)
- action taken
- causality with IMP
- outcome of the adverse event

For AE reporting purposes, no distinction should be made between the IMP and any reference/comparator/placebo product.

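### Section 10.6.5 names only by-visit IOP summaries and no count of study eyes that ever rise by at least 10 mmHg or reach 30 mmHg; later-visit figures may include readings lowered by drops or a stop

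*Combined protocol and SAP*

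**What the plan says.** - **IOP analysis (10.6.5).** "Intraocular pressure will be summarized at each visit, using continuous and discrete summary statistics, including change from baseline and the proportion of study eyes" that rise by 10 mmHg or more, and the proportion at 30 mmHg or more. Both proportions sit inside the by-visit sentence.
- **Actions on IOP (8.2.2).** "If IOP rises above 25 mmHg a topical prostaglandin analog will be considered. If IOP rises above 32 mmHg, the study drug will be discontinued".
- **Follow-up (8.6.2).** "Patients who discontinue study medication generally should be followed through to the final visit".
- **Safety population (10.5).** "No data will be excluded for any reason".
- **Measurement (8.3.1, 8.4.2).** "Intraocular pressure (IOP) will be measured at every visit". Also, "Unscheduled visits are possible at every time and will be documented in the respective CRF"; 10.6.5 does not say where IOP readings from those visits appear.
- **Other capture (8.2, 9.1, 10.6.5).** Concurrent medication is recorded "along with the reason the medication was taken". Section 9.1 adds "Any clinically relevant deterioration in clinical finding is considered an AE and must be recorded", with action taken among the items documented. The TEAE tables in 10.6.5 are cumulative at subject level, by preferred term, with study and fellow eyes separate for ocular events.
- **Rescue rules (10.6.3, 10.6.4).** Both sections state how data after rescue medication are handled for efficacy. 10.6.5 has no corresponding statement for IOP.

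**The concern.** Increased IOP is a named risk of the drug (8.10), and safety is one of the two objectives in section 2. Two features limit what the planned IOP table can show.

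First, an eye that crosses a threshold at Week 4 only and another that crosses at Week 8 only are never added together. The table shows who is above the line at each visit, not how many eyes were ever above it.

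Second, an eye given pressure-lowering drops, or taken off study drug for IOP, stays in later visits with a lowered reading. If DexNP raises IOP, these actions will fall mainly in the DexNP arm. The later-visit table alone then cannot separate a small rise from a larger rise that was treated.

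**Working it through.** The plan states no IOP rate, so there is no plan figure to reproduce. The check asks how far by-visit and any-visit figures could differ, using the two earlier DexNP trials in section 1 as inputs.

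**Step 1. By-visit shares do not fix the any-visit share.** Clinical trial #2 (12 DexNP eyes) reports rises of 5 ± 6, 6 ± 7 and 7 ± 7 mmHg at Weeks 4, 8 and 12. Assuming normality, the share rising by at least 10 mmHg is 1 − Φ((10 − mean)/SD):
- Week 4: (10 − 5)/6 = 0.833, share 0.202
- Week 8: (10 − 6)/7 = 0.571, share 0.284
- Week 12: (10 − 7)/7 = 0.429, share 0.334

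The any-visit share can lie anywhere from the largest of these, 0.334, to their sum, 0.202 + 0.284 + 0.334 = 0.820. With equal between-visit correlation it is 0.382 at 0.9, 0.501 at 0.5 and 0.549 at 0.3. That is about 24 to 35 of 64 DexNP eyes, against at most 21 at any one visit.

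**Step 2. Add the 8.2.2 actions, 12-eye inputs.** Simulation of Weeks 2, 4, 8 and 12 in sequence, 48 scenarios. From the documents: baseline 14 ± 4 and the changes above. Assumed:
- normality, and that the reported means are free of intervention;
- Week 2 change 3 ± 5;
- between-visit correlation 0.5 or 0.9; baseline-change correlation 0 or −0.3;
- drops started after a reading above 25 mmHg with uptake 0, 0.5 or 1, lowering later readings by 4 or 7 mmHg;
- after a reading above 32 mmHg, later readings at baseline + 1 (that trial's value 4 weeks off drug) or lowered by 4 or 7.

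| Quantity, DexNP arm | All scenarios | No drops used |
|---|---|---|
| Drops or stop before Week 12 | 4-36% (3-23 of 64) | 4-9% |
| Week 12 mean rise too low by (7.0 without intervention) | 0.2-2.7 mmHg | 0.2-1.2 mmHg |
| Week 12 share rising ≥10 mmHg (33% without intervention) | 18-33% | 27-33% |
| Any-visit share rising ≥10 mmHg | 32-51% (21-33 of 64) | 38-51% |
| Worst single visit, rising ≥10 mmHg | 18-33% (11-21 of 64) | 27-33% |
| Any-visit IOP ≥30 mmHg | 3-21% | |
| Worst single visit, IOP ≥30 mmHg | 1-11% | |

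**Step 3. Split the gap.** Any-visit minus worst-visit share for the 10 mmHg rise is 6-27 points. The same difference with no intervention (plain accumulation) is 5-18 points; lowering after action adds 1-10. Accumulation is the larger part in most scenarios, and in all those with correlation 0.5. At correlation 0.9 accumulation is only about 0.382 − 0.334 = 0.048, and lowering can exceed it.

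**Step 4. Eyes that trigger nothing in 8.2.2.** Between 0.097 and 0.147 of all eyes (6-9 of 64) rise by at least 10 mmHg at some visit yet never exceed 25 mmHg. They are 0.247-0.350 of the eyes ever rising by that much.

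**Step 5. 19-eye inputs (Clinical trial #1, 4 weeks).** Baseline 15.2 ± 3.1, mean rise 17.4 − 15.2 = 2.2. SD of change = 2.2 × √19 / t, with t on 18 df from p = 0.0015: 2.2 × 4.359/3.74 = 2.56. If that p-value was already multiplied by 3 (Bonferroni), p = 0.0005 gives 2.2 × 4.359/4.23 = 2.27. At one visit (10 − 2.2)/2.56 = 3.04, a share of about 0.001. Held to Week 12 over 96 scenarios: drops or stop before Week 12 in 0.03-6.6% of eyes, mean shortfall at most 0.46 mmHg, any-visit rise of at least 10 mmHg at most 0.43%. This agrees with the Safety profile text in section 1, which reports one rise as high as 8 mmHg and no eye treated for IOP.

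**The case against.** - **The TEAE tables already count eyes that needed action.** Largely true. They are cumulative and at subject level, and 9.1 requires clinically relevant deterioration to be recorded. The two gaps do not compound: an eye with no action has unaltered later readings, and an eye with action should mostly appear as an event. But the TEAE tables rest on the investigator's judgement and do not count the plan's two thresholds. The Step 4 eyes may appear in neither place as a total.
- **The by-visit table is valid.** It is, as a description of IOP under protocol management. Even in the adverse case it would show 18-33% of DexNP eyes up by at least 10 mmHg at the worst visit and a Week 12 mean rise of at least 7.0 − 2.7 = 4.3 mmHg. A reader might infer that the plan hides an IOP effect; the documents do not support that.
- **Lowered readings are only a possibility.** Correct. Drops are to be considered, not required, so it cannot be asserted that later visits will contain them. The any-visit gap remains with no drops used (38-51% against 27-33%).
- **The adverse inputs are weak.** They come from 12 eyes on a taper (three, two, then one drop a day), unlike the constant three a day here. The standard error of the Week 12 mean is about 7/√12 = 2 mmHg, which the ranges do not include, and normality fits poorly in the lower tail.
- **The counts could be made later.** They could, since the data are collected and the thresholds are already fixed. Naming the tables now removes the remaining choice after unmasking, which is a modest gain.
- **The list may not be exhaustive.** 10.6.5 introduces its list as inclusions, and 10.6.4 mentions a separate formal SAP, though only for VFQ-25 scoring. Nothing in the text supplies the counts, but the SAP might.

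**Conclusion.** The point holds in limited form. As written, 10.6.5 names no any-visit IOP count, and by-visit shares cannot supply one. Later-visit means and shares may include lowered readings that the table does not identify.

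The size runs from negligible (19-eye inputs) to material (12-eye inputs: any-visit share 32-51% against 18-33% at the worst visit, Week 12 mean rise 0.2-2.7 mmHg too low). It depends on the assumed normality, correlation, uptake and lowering, and on inputs free of intervention. The figures illustrate a range and do not forecast this trial.

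A reader might go further and conclude that eyes with raised IOP will go unreported, or that the safety conclusion is invalid. Neither follows: most eyes needing action should appear in the TEAE tables, and no success criterion or stopping rule in the documents uses the IOP table. This is a cheap reporting improvement of minor to moderate priority.

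**What to change.** Keep the by-visit table. Add to 10.6.5, per arm and descriptive only, the number and proportion of study eyes with, at any post-baseline visit including unscheduled visits:
- (a) a rise of at least 10 mmHg;
- (b) IOP of at least 30 mmHg;
- (c) start of IOP-lowering medication;
- (d) stop of study drug for IOP, taken from the action recorded for the adverse event.

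In the by-visit table, also give the number of readings taken after (c) or (d). If the formal SAP already contains these counts, a cross-reference is enough.

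The cost is one or two tables from data already collected, and the IOP profile may look less favourable. No between-arm test, composite, change in conduct or change to any clinical trigger is asked for.
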